Cardiorespiratory Fitness and the Apolipoprotein E (ApoE) Genotype and Its Interaction with Cognitive Functions and Cognitive Decline in Late-Middle-Aged Older Adults: A Prospective Study

Principal Investigator: [name]

NTC: NCT05652140
Date: 2022/12/12

Aim:

This study utilized a longitudinal design to examine naturalistic changes in cardiorespiratory fitness (CRF) over an 18-month period as well as the interaction of CRF with apolipoprotein E gene (ApoE4) on a task that modulates inhibitory control demand in a community-dwelling sample of middle age and older adults. Specifically, we conducted a registered analysis using a data-driven 2×2 factorial design to compare changes in behavioral and neuroelectric indices of inhibitory control between four middle aged and older adult groups: (1) ApoE $\epsilon 4$ carriers displaying increases in CRF over 18-months, (2) ApoE $\epsilon 4$ non-carriers displaying increases in CRF over 18-months, (3) ApoE $\epsilon 4$ carriers displaying decreases in CRF over 18-months, and (4) ApoE $\epsilon 4$ non-carriers displaying decreases in CRF over 18-months. It was hypothesized that adults displaying increases in CRF would show more positive changes in inhibitory control outcomes than older adults displaying decreases in CRF. Further, such differences in the outcome measures of inhibitory control between the groups displaying increases and decreases in CRF were hypothesized to be greater in ApoE $\epsilon 4$ carriers.

METHODS

Design and Sample

This prospective study examining CRF and neurocognitive function at baseline and 18-month follow-up in 50–70-year-old adults was registered at ClinicalTrials.gov (NCT05652140). The actual conduct of this study was from 7/1/2018 to 5/1/2021.

Potential participants were recruited via advertisements and personal contact from New Taipei City and Taipei City, Taiwan. Initially, this study included data from 159 participants who were (1) 50–70-years-old, (2) right-hand dominant, did not report (3) psychiatric and neurological disorders, (4) cardiovascular disease, (5) risk of performing physical activities, as measured by Physical Activity Readiness Questionnaire (PAR-Q)¹, had (6) normal color vision, (7) corrected-to-normal or normal vision based on the 20/20 standard, and a (8) Mini-Mental Status Examination (MMSE) score $\geq 25^2$. Due to the substantial overlapping of the study period with the COVID-19 pandemic, a larger-than-expected number of participants withdrew following completion of the baseline stage, resulting in a final sample of 83 with complete data for the registered longitudinal analysis.

Cardiorespiratory fitness assessment

CEF was measured via a braked cycle ergometer (Ergoselect 100/200 Ergoline GmbH, Germany) using the YMCA submaximal test including three or more 3-min

consecutive cycling stages according to ACSM's exercise testing guidelines³. Participants were fitted with a Polar heart rate (HR) monitor (Polar RS800CS; Polar Electro, Kempele, Finland) to continuously monitor their HR and provided ratings of perceived exertion⁴ every two minutes throughout the exercise testing. Participants were instructed to cycle at a power of 25 W (pedaling rate: 50 revolutions per minute [rpm]) for the initial three minutes, and HR recorded at the end of the last minute of the initial 3-min stage was used to determine the workload of the following stages of cycling. The test was terminated if two consecutive steady-state target HRs (i.e., between 110 beat per minute [bpm] and 85% of the age-predicted maximal HR [220 – age]) were reached. Estimated $\dot{V}O_{2\text{max}}$ ($\text{mL}\cdot\text{kg}^{-1}\cdot\text{min}^{-1}$) was then calculated using an established equation³. Participants whose $\dot{V}O_{2\text{max}}$ improved and deteriorated from the baseline to the 18-month follow-up were classified as 'Gaining-Fitness' and 'Losing-Fitness' groups, respectively.

Stroop test

Inhibitory control was assessed via a modified Stroop test in which a 2-cm tall stimulus was focally presented at a time on a black background of a computer at a distance of ~70 cm using Neuroscan Stim2 software (Neurosoft Labs Inc., Sterling, VA, USA). The stimuli included three Chinese words (紅 [RED], 綠 [GREEN]), and 藍 [BLUE] printed in red (RGB: 254, 0, 0), green (RGB: 255, 200, 25), or blue (RGB: 0, 0, 254) inks. Congruent (33%) (e.g., GREEN printed in green color), incongruent (33%) (e.g., GREEN printed in red color), and neutral (33%) (e.g., squares colored in one of the three colors) trials were presented in a randomized sequence using a 500ms stimulus presentation duration and a fixed 2000ms inter-trial interval. Following 10 familiarization trials, participants completed five blocks of 108 trials and were instructed to identify the stimulus color as quickly and accurately as possible by pressing the key corresponding to one of the three colors. After excluding trials with response time < 200ms or > 1200ms⁵, response accuracy and mean response time for congruent and incongruent trials were separately calculated as behavioral outcomes for the subsequent statistical analyses^{5,6}.

Neuroelectric assessment

Electroencephalographic (EEG) data were recorded from a 32-electrode Quik-Cap Neo Net (Compumedics Neuroscan Inc., Charlotte, NC, USA). Data were referenced to the averaged mastoids (M1/M2) using the AFz electrode as the ground, digitalized at a 1000Hz sampling rate, amplified 500 times with a DC to 200Hz filter, and a 60Hz notch filter using a SynAmps2 amplifier. Bipolar electrodes located above and below the left orbit and lateral to the external canthus of each eye were used to monitor electrooculogram. Offline data processing was performed in MATLAB (R2022a, Mathworks Inc.) using the EEGLAB (V8.3)⁷ and ERPLAB (V8.0)⁸ plugins. Following a band-pass filter (IIR Butterworth, 0.1 – 20Hz), bad channels were detected and interpolated using the automatic channel rejection function and the spherical interpolation algorithms in the EEGLAB. Eye-related artifacts were detected and removed by the Step-like Artifacts function of the ERPLAB. EEG epochs were construed from -200 – 1000ms time-locked to the stimulus onset and baseline-corrected using the pre-stimulus period (-200 – 0ms). Epochs displayed step-like artifacts (moving

window width = 200ms, window step = 10ms) or signals that exceeded $\pm 100\mu\text{V}$ were rejected. After visually inspecting the accepted epochs, the mean amplitude P3 components were derived using 400 – 600ms post-stimulus windows, respectively. The Regions of interest was created to investigate parietally (P3/Pz/P4) centered P3 components.

Genetic data collection and processing

Licensed medical technologists collected 2-ml Ethylenediaminetetraacetic acid venous blood samples from the participants. DNA extraction and genotyping were conducted at the Union Clinical Laboratory, Taipei. ApoE genotyping was identified via sequencing rs429358 (ApoE C112R) and rs7412 (ApoE R158C) for three ApoE alleles(s) ($\epsilon 2$, $\epsilon 3$ and $\epsilon 4$) using the real-time polymerase chain reaction. The ApoE4 Carrier group was defined as participants who possessed $\epsilon 3/\epsilon 4$ or $\epsilon 4/\epsilon 4$, while the ApoE4 Non-Carrier group included those who possessed $\epsilon 2/\epsilon 2$, $\epsilon 2/\epsilon 3$, $\epsilon 2/\epsilon 4$, or ApoE $\epsilon 3/\epsilon 3$.

Procedure

Participants were invited to visit the laboratory on two separate days that were 18-month apart. Prior to each laboratory visit, participants were instructed to avoid vigorous exercise for at least 24 hours and consuming alcohol or caffeine at least 6 hours.

Baseline Visit: Participants completed the informed consent, demographic questionnaires, Digit Span Forward and Backward test¹¹, MMSE, PAR-Q, and the computerized Stroop test with simultaneous neuroelectric assessments in a sound-attenuated and dimly lit room, followed by the cardiorespiratory fitness assessment. 18-Month Follow-up Visit: Participants returned to the lab to complete the same protocol at 18 ± 3.32 months after the baseline visit along with a separate visit to the medical clinic to identify ApoE genotypes.

Statistical Analysis Plan:

Analyses were performed using SPSS v.26 (SPSS Inv., Chicago, IL) with a family-wise alpha threshold set at $p = .05$. A two-way ANOVA, with ApoE4 Carriage (Carrier vs. Non-carrier) and changes in CRF (Δ Fitness Group) (Gaining-Fitness vs. Losing-Fitness) as between-subjects factors and Gender as a covariate, was conducted to analyze the demographic and physical outcomes. A similar three-way ANOVA including Congruency (Congruent vs. Incongruent) as an additional within-subjects factor, was used to analyze the baseline cognitive outcomes (response time, response accuracy, and P3 amplitude). A similar three-way ANOVA was conducted to analyze the difference scores for the cognitive outcomes (Δ response time, Δ response accuracy, and Δ P3 amplitude). Greenhouse Geisser and Bonferroni corrections were used when the sphericity assumption was violated and multiple comparisons were required. Effect sizes were reported using partial eta squared (η_p^2) and Cohen's d ¹². The baseline data were presented as means and standard deviations. The change in fitness and neurocognitive outcomes were presented as mean and standard error.

Reference:

1. American College of Sports Medicine. ACSM's Guidelines for Exercise Testing and Prescription. 11th ed. Philadelphia: Lippincott Williams and Wilkins 2022.
3. American College of Sports Medicine. ACSM's guidelines of exercise testing and prescription. 9 ed: Lippincott Williams & Wilkins 2014:1-456.
4. Borg GA. Psychophysical bases of perceived exertion. *Med Sci Sports Exerc* 1982;14:377–81.
6. Rey-Mermet A. Finding an interaction between Stroop congruency and flanker congruency requires a large congruency effect: A within-trial combination of conflict tasks. *Atten Percept Psychophys* 2020;82(5):2271-301. doi: 10.3758/s13414-019-01914-1 [published Online First: 2020/01/25]

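### Follow-up date is not in the model: most follow-ups probably fell in the pandemic with unequal exposure, and calendar time could confound the ΔFitness main effect

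*Combined protocol and SAP*

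**What the plan says.** Design and Sample gives the calendar limits: "The actual conduct of this study was from 7/1/2018 to 5/1/2021". Procedure places the second visit "at 18 ± 3.32 months after the baseline visit". Design and Sample also explains the loss of participants: "Due to the substantial overlapping of the study period with the COVID-19 pandemic", "a larger-than-expected number of participants withdrew following completion of the baseline stage". Of 159 participants at baseline, 83 had complete data.

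The fitness groups are not assigned. Under Cardiorespiratory fitness assessment, a participant is Gaining-Fitness or Losing-Fitness according to the sign of the change in estimated VO2max between the two visits. The cognitive outcomes are difference scores over the same two visits.

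The Statistical Analysis Plan enters ApoE4 carriage and ΔFitness group "as between-subjects factors and Gender as a covariate". The difference-score analysis is described as similar, with Congruency added. Visit date, actual interval and pandemic exposure do not appear in it, and no sensitivity analysis is described.

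**The concern.** The main hypothesis is that people who gain fitness show better change in inhibitory control than people who lose it. Both sides of that comparison are observed over one shared period, so anything in the period that moves fitness and cognition together enters the contrast.

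The plan reports a substantial overlap with the pandemic, and staggered baselines mean that participants would have met different amounts of it before their second visit. If longer exposure tends both to lower fitness and to worsen cognitive change, late-seen participants would gather in the Losing-Fitness group and also show poorer change. Part of a gainers-do-better result would then be early versus late follow-up. Adjusting for Gender does not address this.

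**Working it through.** The plan states no count of follow-ups in the pandemic, so there is no figure of its own to reproduce.

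**1. Inputs from the plan.** Conduct from 7/1/2018 to 5/1/2021; interval 18 ± 3.32 months (3.32 taken as an SD, since it is not labelled); 159 at baseline and 83 analysed, so 159 − 83 = 76 (47.8%) not analysed.

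**Assumptions.** Dates are month/day/year; the pandemic starts between 1 January and 1 April 2020; enrolment is even unless stated otherwise. The plan gives none of these.

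**2. Visit window.** From 1 July 2018 to 1 May 2021 is 34 months. A baseline on the first day plus 18 months gives a follow-up at about 1 January 2020. At 18 − 3.32 = 14.68 months it falls at about 20 September 2019. The last baseline that allows 18 months is about 1 November 2019, so baselines can spread over 34 − 18 = 16 months.

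**3. Share of follow-ups after the assumed onset.** With a fixed 18-month interval, follow-ups cover the 16 months from January 2020 to May 2021. For an onset of 1 April 2020 the share is 13/16 = 81%. The other rows draw the interval from Normal(18, 3.32) and drop visits after study end.

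| Scenario | 1 Jan 2020 | 1 Feb | 11 Mar | 1 Apr |
|---|---|---|---|---|
| Fixed interval, even over 16 months | 99.8% | 93% | 85% | 81% |
| With spread, even over 16 months | 91% | 87% | 81% | 77% |
| With spread, all enrolled in 12 months | 89% | 84% | 76% | 72% |
| With spread, all enrolled in 6 months | 79% | 70% | 57% | 50% |

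Read as day/month/year, the study dates give 65% down to 47% (with spread, even enrolment).

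**4. Variation in exposure.** In the second row, pandemic time before follow-up runs from 0 to 16 months for the earliest onset and from 0 to 13 months for the latest, with an SD of about 4.0 to 4.6 months.

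**5. Date is not the same variable as interval.** With baselines even over 12 to 19 months, the correlation between follow-up date and interval is 0.67 down to 0.38. The variance in date that interval leaves unexplained is 1 − 0.67² = 55% to 1 − 0.38² = 86%.

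**6. Size of a spurious fitness effect.** Suppose there is no true effect and exposure correlates r with VO2max change and r with cognitive change. The two changes then correlate r². Splitting a normal VO2max change at its mean gives

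d = r² × 2√(2/π) / √(1 − r⁴ × 2/π), with 2√(2/π) = 1.596.

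- r = 0.15: 0.0225 × 1.596 = 0.036, d about 0.04.
- r = 0.3: 0.09 × 1.596 / 0.997 = 0.144 (0.145 by simulation), d about 0.15.
- r = 0.45: 0.2025 × 1.596 / 0.987 = 0.327, d about 0.33.

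A simulation with 83 participants and a two-group t-test at two-sided 0.05 (20,000 runs) gives these false-positive rates:

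| r with both changes | 0.1 | 0.2 | 0.3 | 0.4 | 0.5 |
|---|---|---|---|---|---|
| Unadjusted | 5.0% | 5.9% | 9.7% | 21.3% | 44.0% |

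With exposure itself as a covariate, the rate is 4.8% to 5.2% throughout. The test is simpler than the planned three-way ANOVA and covers only the ΔFitness main effect.

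**The case against.** A reader might infer that almost all follow-ups fell in the pandemic. The documents do not support that. They give neither a visit calendar nor an onset date. A share near 100% needs a fixed 18-month interval and an onset at the very start of 2020, and early enrolment or the other date reading brings it to about half or less. The argument needs only that exposure varied.

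A reader might also infer that the plan itself recognises a common cause of fitness change and cognitive change. It does not: Design and Sample connects the pandemic with withdrawal and with nothing else. Nor do the documents show that gainers and losers were seen at different dates, or describe restrictions or activity levels from which a dose-response could be judged.

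The bias is also small unless exposure correlates at about 0.3 or more with both changes, and no value of r comes from the documents. The success of adjustment in the simulation is largely built in, because the covariate there is the exposure itself; a linear date term may track real exposure less well. Finally, the plan is dated December 2022, after conduct ended, and calls the analysis registered, so a new covariate in the main model would be a post hoc change.

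All of this stands. It limits the claim to a possibility and moves the remedy to a sensitivity analysis. It does not remove the gap: the comparison is not randomised, exposure and outcome share one interval, and the plan reports nothing that would let a reader rule calendar time out. Adjusting for interval, which the plan does not do either, would leave most of the variance in follow-up date untouched.

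**Conclusion.** The concern holds as a plausible, unquantified confounder of the ΔFitness main effect. Most follow-ups probably fell in the pandemic: about 77% to 91% under month/day/year dates, even enrolment over 16 months and an onset from January to April 2020, and about half to four-fifths with six-month enrolment. Exposure therefore probably differed between participants.

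The spurious d of about 0.04 to 0.33 rests wholly on assumed correlations of 0.15 to 0.45 with both changes. Only the upper part of that range would distort conclusions much. Bias in the ApoE4 by ΔFitness interaction, the second hypothesis, was not assessed. Nothing here shows that a ΔFitness result would be an artefact, and confidence in the size of any bias is low. The case for acting is that the check is cheap and concerns the main contrast.

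**What to change.** In the Statistical Analysis Plan:

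- Report the distribution of follow-up date by ΔFitness group and by ApoE4 group. If the fitness groups match on date, the concern is largely closed.
- Add a sensitivity analysis, labelled as such, that repeats the difference-score ANOVAs with follow-up date (for example, centred months since 1 January 2020) as a covariate alongside Gender. The registered model stays as it is.
- State in advance that if the ΔFitness result changes materially, it will be reported as not separable from calendar time.

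The cost is one degree of freedom: with 83 participants, four cells and Gender, the between-subjects error falls from 83 − 4 − 1 = 78 to 77. No new data should be needed, because the 18 ± 3.32 months must have been computed from visit dates. Two limits remain. A linear date term is only a proxy for exposure, and the analysis does nothing about selection from the 76 participants not analysed.

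### Participants with the ε2/ε4 genotype hold an ε4 allele but are coded as ApoE4 Non-Carriers, without a stated reason and against the wording of the hypothesis

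*Combined protocol and SAP*

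**What the plan says.** The Aim sets up four groups by crossing ε4 carriage with gain or loss of cardiorespiratory fitness; the fourth is "ApoE $\epsilon 4$ non-carriers displaying decreases in CRF over 18-months". The second hypothesis is that differences between those gaining and those losing fitness "were hypothesized to be greater in ApoE $\epsilon 4$ carriers". The Statistical Analysis Plan enters the genotype as the two-level factor "ApoE4 Carriage (Carrier vs. Non-carrier)" in every ANOVA it describes.

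The coding rule is in Genetic data collection and processing. Participants are typed "for three ApoE alleles(s) ($\epsilon 2$, $\epsilon 3$ and $\epsilon 4$) using the real-time polymerase chain reaction". Only two of the resulting genotypes, ε3/ε4 and ε4/ε4, make a participant a carrier. All others fall on the opposite side: "the ApoE4 Non-Carrier group included those who possessed $\epsilon 2/\epsilon 2$, $\epsilon 2/\epsilon 3$, $\epsilon 2/\epsilon 4". The fourth genotype listed there is ε3/ε3.

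The document gives no reason for placing ε2/ε4 with the non-carriers, no genotype counts, and no analysis that recodes or omits that genotype.

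**The concern.** A reader of the Aim or the Statistical Analysis Plan will take non-carrier to mean no ε4 allele. Under the coding rule it means no ε4 allele, or one ε4 paired with ε2. If even one of the 83 is ε2/ε4, the group reported as ε4 non-carriers contains an ε4 holder, and the interaction test does not answer the second hypothesis as worded.

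ε4 holders are probably the smaller group and are divided again by fitness change, so one or two people weigh more there than in the full 83.

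Timing adds a question of transparency. Under Design and Sample, "The actual conduct of this study was from 7/1/2018 to 5/1/2021", and the document is dated 2022/12/12. The grouping could therefore have been fixed with genotypes known. The document does not say that it was.

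**Working it through.** **1. Does the rule cover every genotype?** Three alleles give six genotypes.

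| Genotype | Has ε4? | Coded as |
|---|---|---|
| ε2/ε2 | no | Non-Carrier |
| ε2/ε3 | no | Non-Carrier |
| ε3/ε3 | no | Non-Carrier |
| ε2/ε4 | **yes** | **Non-Carrier** |
| ε3/ε4 | yes | Carrier |
| ε4/ε4 | yes | Carrier |

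The rule is complete and does not overlap. Exactly one genotype is coded against its label.

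**2. How many people might be affected?** The analysed sample of 83 is from Design and Sample. Allele frequencies are not in the document. I assume ε4 (p4) at 0.06–0.14, ε2 (p2) at 0.05–0.10, and Hardy-Weinberg proportions.

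- Expected ε2/ε4: 83 × 2 × p2 × p4. Low: 83 × 0.006 = 0.50. High: 83 × 0.028 = 2.32.
- Chance of at least one: 1 − (1 − 2·p2·p4)^83. Low: 1 − 0.994^83 = 0.39. High: 1 − 0.972^83 = 0.91. So the chance of none is 9–61%.
- Chance of two or more: 0.09–0.68.
- All ε4 holders: 83 × [1 − (1 − p4)²] = 9.7 to 21.6.
- ε2/ε4 as a share of ε4 holders: 2·p2/(2 − p4) = 0.10/1.94 = 5% to 0.20/1.86 = 11%.
- ε2/ε4 as a share of the planned Non-Carrier group: 0.006/0.8896 = 0.7% to 0.028/0.7676 = 3.7%.

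Wider assumptions (ε2 0.03–0.10, ε4 0.05–0.15) give 0.25 to 2.5 expected and a 22–92% chance of at least one.

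**3. Effect on the interaction contrast.** Let C be the number of ε4 holders and k the number who are ε2/ε4. I take two cases: C = 13 with k = 1, and C = 20 with k = 2.

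- If ε2/ε4 behave as carriers, the planned coding shrinks the contrast by k/(83 − C + k): 1/71 = 1.4%, and 2/65 = 3.1%.
- Standard-error ratio, planned to recoded, with balanced fitness groups: √[(1/12 + 1/71)/(1/13 + 1/70)] = 1.033, and √[(1/18 + 1/65)/(1/20 + 1/63)] = 1.038.
- If ε2/ε4 behave as non-carriers, the planned coding loses nothing and recoding shrinks the contrast by k/C: 1/13 = 7.7%, and 2/20 = 10%.

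**4. Power if ε2/ε4 behave as carriers.** The document states no effect size, so both effects below are assumptions: the extra gaining-minus-losing difference in carriers, in outcome SDs. The figures come from 12,000 simulated datasets per scenario, for one between-subjects outcome. The model was linear, with ApoE4, fitness group, their interaction and Gender, tested two-sided at 0.05.

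| Effect | C, k | Any-ε4 coding | Planned coding |
|---|---|---|---|
| 0.8 SD | 13, 1 | 0.23 | 0.21 |
| 0.8 SD | 20, 2 | 0.33 | 0.29 |
| 1.28 SD | 13, 1 | 0.52 | 0.48 |
| 1.28 SD | 20, 2 | 0.67 | 0.60 |

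A second simulation of 8,000 datasets per scenario agreed to within 0.01.

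**The case against.** The strongest reply is that the genetics section is the operational definition. It assigns every genotype once, two analysts would code everyone identically, and the Aim and Statistical Analysis Plan use only a short label with no competing list. On that view the fault is loose labelling and a missing justification. It is true that the rule is clear and reproducible. But a clear rule does not make the label true, and the hypothesis is written in terms of the label.

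The second reply is about size. There may be no ε2/ε4 participant at all, and with one or two the loss is slight. The low power in the scenarios comes mainly from having few carriers among 83. All of that stands. The largest drop, 0.67 to 0.60, pairs a count near the top of the assumed range with the larger assumed effect.

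The third reply is about the remedy. Recoding costs more if it is wrong (7.7–10%) than the planned coding does (1.4–3.1%), and it would be done after data collection in an analysis described as registered. This is a good reason to disclose any recode, to name one grouping as primary and to show the planned grouping beside it. It does not justify leaving the mismatch in place. Nor does the lack of reported counts count against the plan in itself, since counts are results; they are simply what is needed to settle the point.

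**Conclusion.** The concern holds. As written, any ε2/ε4 participant would be analysed and reported as an ε4 non-carrier, which is at odds with the trial's own hypothesis and factor name, and nothing in the document explains it. That finding rests on the text alone.

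The numerical consequence is conditional and probably small. It is nil if none of the 83 is ε2/ε4. With one or two who behave as carriers, it is a contrast 1.4–3.1% smaller, a standard error 3–4% larger, and power lower by 0.02 to 0.07 in the scenarios tried. These sizes rest on assumed allele frequencies, carrier counts and effect sizes. The document does not settle whether ε2/ε4 participants behave like other ε4 holders, so neither grouping can be shown from it to be the more accurate one. The point should be fixed because the second hypothesis depends on this factor and the correction is nearly free.

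**What to change.** 1. Report how many of the 83 are ε2/ε4. If none, say so and correct the definition; no rerun is needed.
2. If there are any, match the factor to the hypothesis: Carrier is ε2/ε4, ε3/ε4 or ε4/ε4, and Non-Carrier is ε2/ε2, ε2/ε3 or ε3/ε3. Name this as the primary grouping.
3. State that the recode was made after data collection had ended. Show the results under the planned grouping alongside, plus a sensitivity analysis that leaves out ε2/ε4.
4. If the present grouping is deliberate, give the reason and rename the factor, groups and hypothesis to fit, for example ε3/ε4 or ε4/ε4 versus all other genotypes. The other groupings then become labelled sensitivity analyses.

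The cost is a few lines of text, recoding of probably zero to two or three participants already genotyped, and at most two reruns beside the planned analysis.

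### The plan claims a family-wise alpha of .05 but defines neither the family nor what Bonferroni covers; on its most natural reading the 5% is not delivered

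*Combined protocol and SAP*

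**What the plan says.** The Statistical Analysis Plan section opens by setting the error rate: the analyses were run "with a family-wise alpha threshold set at $p = .05". Its only statement on multiplicity is "Greenhouse Geisser and Bonferroni corrections were used when the sphericity assumption was violated and multiple comparisons were required". It gives no list of tests, divisor or adjusted threshold.

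A three-way ANOVA (ApoE4 carriage, fitness-change group, Congruency) is used to "analyze the difference scores for the cognitive outcomes", and three outcomes are listed: change in response time, in response accuracy and in P3 amplitude. None is called primary and no order of testing is given.

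The Aim states two directional hypotheses:
- Fitness-change effect (ΔFitness): "adults displaying increases in CRF would show more positive changes in inhibitory control outcomes than older adults displaying decreases in CRF".
- Interaction with genotype (ΔFitness×ApoE4): "such differences in the outcome measures of inhibitory control between the groups displaying increases and decreases in CRF were hypothesized to be greater" in ε4 carriers.

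The Aim also says "we conducted a registered analysis". Design and Sample states: "The actual conduct of this study was from 7/1/2018 to 5/1/2021". The document is dated 2022/12/12.

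**The concern.** A family-wise rate means something only for a stated set of tests. Here two hypotheses on three outcomes give at least six F tests, and nothing in the text says that they share one 5%.

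The Bonferroni sentence sits beside Greenhouse-Geisser, as a procedural note on running an ANOVA in SPSS. Read that way, it adjusts follow-up comparisons within one ANOVA and leaves each F test at .05. The Greenhouse-Geisser half adds no protection, because the only within-subjects factor has two levels and sphericity cannot then be violated.

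At stake is how a single positive result is read. With no primary outcome, a significant ΔFitness or ΔFitness×ApoE4 effect on any one outcome could be reported as support at a family-wise 5% when the actual rate is two to five times that.

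**Working it through.** **Inputs from the document.** Alpha .05; two hypotheses (Aim); three change outcomes (Statistical Analysis Plan); N = 83 (Design and Sample); two-level factors throughout; Gender as covariate.

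**Inputs assumed, because the document does not give them.** 13 to 41 carriers of 83; 35% or 50% gainers; correlation between outcomes 0 to 0.8.

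**1. The plan's own figure.** The .05 can be neither reproduced nor refuted without a divisor. It is met if Bonferroni spans exactly the family tested. With independent tests:
- 3 tests at .05/3 = .0167: 1 − (1 − .0167)^3 = 4.9%
- 6 tests at .05/6 = .0083: 1 − (1 − .0083)^6 = 4.9%

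**2. Each F test at .05, independent tests.** The rate is 1 − 0.95^m:
- one hypothesis, three outcomes: 1 − 0.95^3 = 14.3%
- both hypotheses, three outcomes: 1 − 0.95^6 = 26.5%

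**3. Allowing for correlation and unequal cells.** A null simulation used N = 83, a gender covariate, and type III tests on the change score averaged over Congruency, which is what the between-subject effects of the mixed ANOVA test. There were 32 settings (carriers 13, 20, 30, 41; gainers 35%, 50%; correlation 0, 0.2, 0.5, 0.8) with 20,000 runs each. Ranges over settings:
- ΔFitness on three outcomes: 9.6-14.7%
- ΔFitness×ApoE4 on three outcomes: 9.7-14.8%
- both (six tests): 15.9-26.4%

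Values slightly above 14.3% are simulation noise, so I report about 10-14%.

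A second, separate simulation (50:50 gainers and losers, 20,000 runs per setting) gave these six-test rates:

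| Assumed carriers | corr. 0 | 0.3 | 0.5 | 0.8 |
|---|---|---|---|---|
| 50% | 26.5% | 26.2% | 23.6% | 18.5% |
| 30% | 25.0% | 24.3% | 22.5% | 17.9% |
| 20% | 23.7% | 22.9% | 20.7% | 16.6% |
| 15% | 22.8% | 22.2% | 19.9% | 16.0% |

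Fewer carriers lower the rate because the main-effect and interaction tests become correlated.

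**4. Predicted direction only.** If only effects in the hypothesised direction count, independent tests give 1 − 0.975^3 = 7.3% and 1 − 0.975^6 = 14.1%. The first simulation gave 4.7-7.7% for three tests and 7.9-14.0% for six. The benchmark is about 2.5%, half of a two-sided 5%.

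**5. If the Congruency interactions also count.** Adding ΔFitness×Congruency and ΔFitness×ApoE4×Congruency makes 4 effects × 3 outcomes = 12 tests: 1 − 0.95^12 = 46.0% if independent.

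**6. If Bonferroni was meant across F tests, the divisor still matters.** Six tests at .0167 give 1 − (1 − .0167)^6 = 9.6% (simulated 6.0-9.9%). Six tests at .0083 give a simulated 3.1-5.0%.

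**7. If one primary outcome was fixed elsewhere.** Both hypotheses on a single outcome at .05 give 1 − 0.95^2 = 9.75% if independent.

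**The case against.** The strongest reply is that the alpha sentence and the Bonferroni sentence belong together: the authors set a family-wise .05 and used Bonferroni to deliver it. Since every factor has two levels, few pairwise comparisons are left for Bonferroni to adjust, which lends this some weight. It stands as a possible reading. A reader might infer that the plan certainly inflates the error rate, or that the rate is 26.5%. The document supports neither. What is certain is that the family and the divisor are missing; the inflation depends on an inferred scope, and 26.5% requires independent tests.

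Six tests is also a choice of family. The study concerns a task that varies inhibitory demand, so the Congruency interactions may carry the hypotheses better than an effect averaged over trial types. This stands. It means that 16-26% is not an upper bound, and that nothing in the document justifies ranking those interactions below the between-subject effects.

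The hypotheses are directional, so either-direction rates overstate the chance of false support in absolute terms. This too stands, but the ratio to the 2.5% benchmark is similar.

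The registered analysis may fix a primary outcome that this document does not mention. Two hypotheses on it would still exceed 5% if each were tested at .05.

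Finally, a reader might infer from the dates that the tests were chosen with the results in hand. The document shows only that it postdates the end of the study; it does not say what was known when the analysis was fixed.

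**Conclusion.** The point holds in conditional form. The family-wise claim is undefined as written. On the most natural reading of the Bonferroni sentence it is wrong by a factor of about two to three for one hypothesis on three outcomes (10-14%), and about three to five for both hypotheses on the six between-subject tests (16-26%). In the predicted direction only, the rates are about 5-8% and 8-14% against 2.5%. All these figures are for the global null and rest on assumed carrier numbers, gainer shares and outcome correlations of 0 to 0.8. High correlation does not remove the problem: at 0.8 the six-test rate is still at least about 16%.

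If Bonferroni in fact spans all the hypothesis tests, the claim is sound and only the divisor needs stating.

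**What to change.** Unless a correction across the F tests was in fact applied, replace the family-wise phrase with: *per-test alpha .05, unadjusted across outcomes and effects; Bonferroni applied to follow-up comparisons within each ANOVA*. Describe significant results on single outcomes as exploratory. This takes one or two sentences and no new analysis; the cost is that the family-wise claim is given up.

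If a correction across the F tests was applied, state the tests it covered and the divisor.

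If the authors want to keep the family-wise claim, they should:
- name their own family, saying whether the ΔFitness×Congruency and three-way terms belong to it;
- apply Holm at .05 across that family, using p-values from the existing F tests;
- disclose that the document (2022/12/12) postdates the end of the study (5/1/2021).

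For a six-test family, Holm gave a simulated rate of 3.1-5.0%. The cost is power, since the smallest p must be at most .05/6 = .0083 (.05/12 = .0042 for twelve tests); later Holm steps are less strict. Illustrative power for a single test, with 78 error df, the same carrier and gainer settings, and effects in residual SD of the averaged change score:
- assumed ΔFitness effect of 0.5 SD: 35-61% at .05, falling to 14-33% at .0083;
- assumed ΔFitness×ApoE4 difference of 0.8 SD: 24-43%, falling to 8-19%.

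A family named at this stage is also weaker than one fixed before data collection.
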